### **3.5. Withdrawal Criteria**

An interim analysis is planned at recruitment of 50% of the patients (n=59) and if first trimester ultrasound is not completable in at least 50% of patients, the study will be stopped. An individual patient may withdraw from the study at any time.

### **3.6. Subject Replacement**

Subjects who withdraw from the study will be replaced.

## **4. TRIAL SCHEDULE**

|                            |   |
|----------------------------|---|
| September 2020 - June 2021 | Recruitment                               |
| December 2020              | Goal: 25% recruitment at end of month     |
| February 2021              | Goal: 50% recruitment at end of month     |
| May 2021                   | Goal: 75% of recruitment mid-month        |
| July 2021-August 2021      | Follow up on delivery records, clean data |
| August 2021                | Data analysis, review by entire team      |
| September - November 2021  | Manuscript preparation                    |
| December 2021              | Manuscript submission                     |

#### **4.1. Randomization and Blinding**

Randomization will be carried out in a 1:1 ratio with block size 4, stratified into three groups by pre-pregnancy BMI (see below) using RedCap.

Group 1 (First trimester ultrasound)

[figure not shown]
- BMI 35-39.9: 19 patients
- BMI 40-44.9: 20 patients
- BMI >45: 20 patients

Group 2 (Second trimester anatomy ultrasound)

- BMI 35-39.9: 19 patients
- BMI 40-44.9: 20 patients
- BMI >45: 20 patients

There is no plan for breaking of randomization codes, as randomization will be done through RedCap, nor are there plans for unmasking.

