**3.2. Criteria for Recruitment**

Once a potential subject expresses interest in participation, she will be asked to undergo a brief ultrasound to verify her gestational age. This ultrasound will be free of charge, will take approximately 5 minutes, and will not be entered in her medical record or saved as study images. This is to confirm viability gestational age, and number of fetuses.)

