#### **4.2. Study Flow Diagram**

#### **4.3. Study Visits and Procedures**

##### *a. Screening Visits and Procedures*

Research staff will screen the schedules of the ultrasound clinics at Memorial City, Bellaire, UT Professional Building, LBJ, and Harris Health Aldine ultrasound clinics for patients undergoing clinically indicated ultrasounds before 14 weeks gestational age. (These existing clinic visits are usually for dating ultrasound or nuchal translucency, an early assessment of a marker of aneuploidy.) Research staff will approach patients at these visits and describe the study. If the patient is interested in participation, the sequence of events that should occur include confirmation of eligibility with a 5-minute ultrasound to determine a single viable fetus before 14 weeks. This is the only procedure necessary before recruitment. If the patient is eligible according to this screening ultrasound, she can be randomized at that time.

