##### *b. Study Visits and Procedures*

After the screening ultrasound confirms eligibility and a patient is given informed consent, the patient can then be randomized. If the patient is randomized to the intervention (detailed first trimester anatomy ultrasound), this scan is performed at the randomization visit if the patient is between 12w0d and 13w6d. If she is less than 12w0d, a separate study visit is scheduled for a date at her convenience during the days she is between 12w0d and 13w6d. A dedicated room and time slots have been made available for these study visits at Memorial Hermann Southwest and at the Fetal Center at UTPB. This separate scan/visit is not billed as it is not part of the standard of care.

After this detailed research ultrasound, which will be limited to 15 minutes, she then receives her clinically indicated dating ultrasound or nuchal translucency measurement. The total estimated time of all these ultrasounds is expected to be approximately 30 minutes, with breaks in between to allow the patient some movement and the opportunity to use the rest room, and to allow the exchange of operators (research staff vs clinical staff) and the creation of distinct records (research ultrasound is not saved to electronic medical records, so a new scanning encounter must be opened for the clinical ultrasound that day). The patient will complete a survey about her satisfaction with this technique via email. In addition, as a safety measure, if an anomaly is suspected on the day of the detailed first trimester anatomy scan, the patient will be unblinded. The research team will inform the clinical team so that a more detailed evaluation can be done and so that this information can enter the clinical record and affect clinical management.

Patients randomized to the intervention arm are later scheduled for a second trimester ultrasound by the clinical team, as this is part of standard obstetrical care. Research staff will ensure patients have this scan scheduled and completed, as it is part of study procedure. Data about this scan will be recorded in the patient's research record. This scan can be repeated as indicated according to UT's protocol for assessing anatomy.

If the patient is randomized to the comparison arm, she does not undergo a detailed first trimester ultrasound that day, but she does receive her clinically indicated limited ultrasound for dating or for nuchal translucency. She then undergoes a second

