## 6. BLINDING

Patients are not blinded to their group as they are aware of the timing of their detailed ultrasound. The clinical team will not be informed of the patient's randomization assignment, images from research ultrasounds will not be available to the clinical team, and the clinical team will not be made aware of whether the second trimester scan done by them is for comparison to the gold standard (the GSS in intervention arm patients) or for anatomy (in comparison arm patients).

Patients and the care team will be unblended from the results of the first trimester exam if there is an anomaly. There are no other plans for unblinding.

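### A single printed block size of 4, with unmasked recruiters and a short scan before randomisation, lets a well-informed recruiter predict up to one third of allocations

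*Combined protocol and SAP*

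**What the plan says.** Section 4.1 states the scheme: "Randomization will be carried out in a 1:1 ratio with block size 4", "stratified into three groups by pre-pregnancy BMI (see below) using RedCap". The strata hold 38, 40 and 40 women. Clinic is not a stratification factor, so each BMI stratum has one sequence for all clinics. The section does not vary the block size, withhold it from recruiters, or say who prepares the list.

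Section 4.3.a has research staff approach patients at several clinics. Eligibility rests on "confirmation of eligibility with a 5-minute ultrasound to determine a single viable fetus before 14 weeks". Section 4.3.b gives the order: "After the screening ultrasound confirms eligibility and a patient is given informed consent, the patient can then be randomized". The timing is permissive: "If the patient is eligible according to this screening ultrasound, she can be randomized at that time". Section 3.2 says that the screening scan "will not be entered in her medical record or saved as study images".

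On masking, section 6 says: "Patients are not blinded to their group as they are aware of the timing of their detailed ultrasound". The same section masks the clinical team, which performs the second trimester scans. Section 4.3.b has research staff perform the first trimester research scan, so they learn who is in that arm. Section 8.1 gives the whole study team access to study documents in RedCap. No section says who can see past allocations or who performs the screening scan.

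**The concern.** RedCap hides the next assignment but does not stop anyone inferring it from earlier ones. With a known block of 4, the last assignment in each block follows from the first three, and the third follows from the first two when those match.

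Here that knowledge could coincide with information about the woman. The screening scan comes before consent and randomisation, so whoever sees it may form a view of how easily the fetus images. A woman who looks difficult could be deferred, or not pursued, when the next assignment is known. Deferral breaks no rule in the plan, and because no screening images are kept, a later audit could not show what was seen. The primary outcome is the proportion of complete scans. Selection on ease of imaging, if it happened, would therefore act on the primary comparison.

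**Working it through.** The documents give no predictability figure to reproduce. The inputs are the block size of 4, the 1:1 ratio and the strata from section 4.1 (19 + 19 = 38, 20 + 20 = 40, 20 + 20 = 40; total 118), and the planned rates of 70% and 85% from section 9.1.

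**1. Certain allocations when every earlier allocation is known.** A block of 4 has 6 equally likely orders.
- Slots 1 and 2 are never certain.
- Slot 3 is certain if the first two match: probability 2/6 = 1/3.
- Slot 4 is always certain.
- Share certain: (0 + 0 + 1/3 + 1)/4 = 1.333/4 = 33.3%.
- Over the planned strata: 9 full blocks plus 2 women give 9 × 1.333 = 12.0; 10 blocks give 13.33, twice. The total is 38.7 of 118, or 32.8%.

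**2. Best-guess accuracy under the same knowledge.** By slot it is 1/2, 2/3, 2/3 and 1, so 2.833/4 = 70.8%. Simple randomisation gives 50%.

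**3. Partial knowledge.** Suppose the recruiter knows the position in the block but sees each earlier allocation only with probability f.
- Slot 3 is certain with probability f²/3.
- Slot 4 is certain if all three earlier ones are seen (f³), or if exactly two are seen and match: 3f²(1 − f) × 1/3 = f²(1 − f). The sum is f².
- Share certain: (f²/3 + f²)/4 = f²/3.

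| f (assumption) | Share certain |
|---|---|
| 1 | 33% |
| 0.8 | 21% |
| 0.5 | 8% |
| 1/3 | 4% |

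A recruiter who cannot locate the block boundaries knows less than this.

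**4. Alternative block schemes.** Fixed sizes were enumerated. Random mixtures were simulated (3,000 strata of 40 women) for an observer who knows the set of sizes and all earlier allocations, and who updates the probability of each position in the block.

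| Scheme | Certain | Best guess right |
|---|---|---|
| Fixed 4 (plan) | 33% | 71% |
| Fixed 6 | 25% | 68% |
| Fixed 8 | 20% | 67% |
| Random 4, 6 | 6% | 69% |
| Random 4, 6, 8 | 2% | 68% |

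Out of 118, random 4 and 6 leaves about 7 certain (0.0595 × 118), and random 4, 6 and 8 about 3 (0.0243 × 118).

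**5. Possible shift in the estimate (assumption).** If steering opens a completion gap g between arms in the certain slots only, the expected shift is the share certain times g.
- f = 1: 0.328 × 10 = 3.3 points; 0.328 × 20 = 6.6 points.
- f = 0.5: 0.083 × 10 = 0.8 points; 0.083 × 20 = 1.7 points.

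A simulation with a true 70% in both arms and f = 1 gave shifts of 3.4 and 6.7 points. The two-sided chi-square test rejected in 6.8% and 12.8% of 6,000 trials, against 5.7% with no steering. The planned difference is 15 points.

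**The case against.** The strongest case against runs as follows. One third requires knowledge of the block size and of every earlier allocation in a stratum whose sequence runs across several clinics, and no section says recruiters have it. The clinical team is masked, and it performs the scans that form the comparison arm's primary outcome. The screening look is brief (5 minutes in section 4.3.a, 2 minutes in section 7.1) and serves to confirm viability, gestational age and fetal number. The comparison arm's outcome is measured from 18w0d, at least four weeks after the recruitment window closes. Women below 12w0d have even the first trimester scan at a later visit. BMI, which the documents name as the source of difficulty, is already a stratification factor.

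Most of this stands as a limit on size. A reader might infer that the trial is unblinded throughout, that one third of allocations will be certain, or that the estimate will be biased. The documents support none of these: masking is partial, one third is a ceiling, and nothing shows that the short look predicts completion.

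It does not close the route. Access to study documents in RedCap makes a view of past allocations plausible. With 118 women over the 10 months in section 4 or the 2 years in section 9.1, each stratum gains about 118/(3 × 10) = 3.9 or 118/(3 × 24) = 1.6 women a month, few enough to remember. Women at 12w0d to 13w6d in the intervention arm have the outcome scan at the same visit. Section 1.1 attributes second trimester difficulty to maternal adipose tissue, which persists, and the top BMI stratum has no upper limit.

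**Conclusion.** The weakness is real but bounded. The fixed, printed block size allows up to 33% certain allocations (about 39 of 118) and a best guess right 71% of the time. Both figures assume a recruiter who knows the block size and all earlier allocations in the stratum; at half visibility the certain share is about 8%. Nothing in the plan prevents this knowledge, and nothing states that recruiters have it.

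Any effect on the completion-rate difference rests on two further assumptions: that the short look is informative, and that someone acts on it. Under an assumed 10 to 20 point gap in the certain slots, the shift is about 3 to 7 points at most-informed visibility and 1 to 2 points at half visibility. This is a preventable exposure that should be closed, not evidence of bias.

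**What to change.** - Build the RedCap allocation table with randomly varying block sizes, for example 4, 6 and 8, within each BMI stratum. If enrolment has begun, apply this to the remaining allocations.
- Have the table prepared by someone who neither recruits nor scans, and say so in section 4.1.
- Move the block sizes out of the protocol text that recruiters hold and into a restricted document.
- Withhold the running allocation list from recruiters, and state who can see it. Varying the blocks removes most certainty but leaves an informed best guess at 68% to 69%, so this step carries as much weight as the first. It cannot hide the assignments a recruiter learns from her own patients.
- State who performs the screening scan.

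The cost is a new table and a few lines of protocol text. The statistical price is a possible end-of-stratum imbalance of up to 3 women per stratum with blocks of 4 and 6, or up to 4 if a block of 8 is included, against up to 2 now. Over three strata the extremes are 9 or 12, against 6. Exact balance is not guaranteed today either: 38 is not a multiple of 4, so 19 against 19 in the lowest stratum has probability 4/6, and otherwise the split is 20 against 18.

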#### **4.2. Study Flow Diagram**

#### **4.3. Study Visits and Procedures**

##### *a. Screening Visits and Procedures*

Research staff will screen the schedules of the ultrasound clinics at Memorial City, Bellaire, UT Professional Building, LBJ, and Harris Health Aldine ultrasound clinics for patients undergoing clinically indicated ultrasounds before 14 weeks gestational age. (These existing clinic visits are usually for dating ultrasound or nuchal translucency, an early assessment of a marker of aneuploidy.) Research staff will approach patients at these visits and describe the study. If the patient is interested in participation, the sequence of events that should occur include confirmation of eligibility with a 5-minute ultrasound to determine a single viable fetus before 14 weeks. This is the only procedure necessary before recruitment. If the patient is eligible according to this screening ultrasound, she can be randomized at that time.

##### *b. Study Visits and Procedures*

After the screening ultrasound confirms eligibility and a patient is given informed consent, the patient can then be randomized. If the patient is randomized to the intervention (detailed first trimester anatomy ultrasound), this scan is performed at the randomization visit if the patient is between 12w0d and 13w6d. If she is less than 12w0d, a separate study visit is scheduled for a date at her convenience during the days she is between 12w0d and 13w6d. A dedicated room and time slots have been made available for these study visits at Memorial Hermann Southwest and at the Fetal Center at UTPB. This separate scan/visit is not billed as it is not part of the standard of care.

After this detailed research ultrasound, which will be limited to 15 minutes, she then receives her clinically indicated dating ultrasound or nuchal translucency measurement. The total estimated time of all these ultrasounds is expected to be approximately 30 minutes, with breaks in between to allow the patient some movement and the opportunity to use the rest room, and to allow the exchange of operators (research staff vs clinical staff) and the creation of distinct records (research ultrasound is not saved to electronic medical records, so a new scanning encounter must be opened for the clinical ultrasound that day). The patient will complete a survey about her satisfaction with this technique via email. In addition, as a safety measure, if an anomaly is suspected on the day of the detailed first trimester anatomy scan, the patient will be unblinded. The research team will inform the clinical team so that a more detailed evaluation can be done and so that this information can enter the clinical record and affect clinical management.

Patients randomized to the intervention arm are later scheduled for a second trimester ultrasound by the clinical team, as this is part of standard obstetrical care. Research staff will ensure patients have this scan scheduled and completed, as it is part of study procedure. Data about this scan will be recorded in the patient's research record. This scan can be repeated as indicated according to UT's protocol for assessing anatomy.

If the patient is randomized to the comparison arm, she does not undergo a detailed first trimester ultrasound that day, but she does receive her clinically indicated limited ultrasound for dating or for nuchal translucency. She then undergoes a second

trimester ultrasound by the clinical team as part of standard obstetrical care and completes a survey regarding her satisfaction with this technique via email. Research staff will ensure patients have this scan scheduled and completed, as it is part of study procedure. Data about this scan will be recorded in the patient's research record. This scan can be repeated as indicated according to UT's protocol for assessing anatomy.

*c. Final Study Visit:*

The final study visit is denoted by completion of the second trimester gold standard scan (GSS) for patients randomized to the intervention arm, and at the completion of the second trimester anatomy ultrasound for patients randomized to the comparison arm. Participants will continue to be followed through their pregnancy to document the number of ultrasounds required to complete the fetal anatomy evaluation.

*d. Post Study Follow up and Procedures*

Medical records will be reviewed after each study participant's due date to assess whether delivery has occurred and to record delivery outcomes from the medical records, when available. This is chiefly so that a post-natal evaluation can be recorded to confirm or exclude anatomical anomalies. Delivery outcomes are not a primary outcome and request of outside delivery records will not be required for a subject's record to be marked as completely collected.

Adverse outcomes, including discomfort during ultrasound as well as neonatal outcomes, will be recorded in the subject's research record.

*e. Discontinuation Visit and Procedures*

Subjects may withdraw voluntarily from participation in the study at any time. Subjects may also withdraw voluntarily from receiving the study intervention for any reason.

If a patient in the intervention arm withdraws from the study during to her first trimester anatomy ultrasound, she will be asked to complete the survey regarding her experience regardless of the duration of the first trimester ultrasound. She will then undergo her clinically indicated ultrasound (which are not transvaginal).

If a subject in the intervention arm withdraws from the study prior to her second trimester GSS ultrasound (done as "back up" for the intervention), a standard email will be sent to her confirming her withdrawal and encouraging her to seek a second trimester (standard of care) anatomy ultrasound as the anatomy evaluation she had in the first trimester is considered experimental.

If a subject in the comparison arm withdraws from the study prior to her second trimester anatomy ultrasound, she will not be required to complete the survey about her experience. A standard email will be sent to her confirming her withdrawal and encouraging her to seek a second trimester (standard of care) anatomy ultrasound outside the study.

If voluntary withdrawal occurs, the subject will be given standard care under medical supervision until the symptoms of any adverse event resolve or the subject's condition becomes stable.

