**d. Rationale for Dating Ranges and Images Required**

Required images in the first trimester anatomy ultrasound (the intervention) were selected based on peer-reviewed literature on the subject of early fetal anatomy assessment. A detailed list of images required in the intervention is appended. The following is a list of required planes and peer-reviewed literature to support their use as key in the evaluation of major and minor fetal anomalies. This list of planes is deemed sufficient by multiple experts in the field and the International Society for Ultrasound in Obstetrics and Gynecology, or ISUOG (14, 19).

1. Midsagittal fetus
2. Placental cord insertion
3. Profile
4. Lateral ventricles
5. BPD (transthalamic view)
6. Head circumference
7. Posterior fossa (cerebellum)
8. Orbita
9. Face (including retronasal triangle)
10. Heart rate
11. Situs
12. Four chamber heart
13. 3 vessel view
14. Bladder
15. Kidneys
16. Abdominal circumference
17. Fetal cord insertion
18. 3 vessel cord
19. Extremities
20. Spine

The first trimester required images largely correspond with second trimester required images, with very few differences which reflect that some structures (e.g. the lip) are hard to see in the first trimester, and are replaced by a feasible alternative (e.g. the retronasal triangle) based on peer-reviewed literature.

IRB NUMBER: HSC-MS-20-0895  
IRB APPROVAL DATE: 08/12/2021

All ultrasounds performed in the second trimester, both the GSS for the intervention arm and the anatomy evaluation in the comparison arm, will be evaluated for completion based on UT's proprietary second trimester protocol, which abides by standards set out by the International Society of Ultrasound in Obstetrics & Gynecology (ISUOG) and the American Institute of Ultrasound in Medicine (AIUM) (20, 22-23). A list of images required for the comparison is given here in brief.

1. Fetal position
2. Placental cord insertion
3. Profile
4. Lateral ventricles
5. BPD (transthalamic view)
6. Head circumference
7. Posterior fossa (cerebellum)
8. Choroid plexus
9. Orbita
10. Face
11. Nose-lips
12. Heart rate
13. Heart rate
14. Situs
15. Four chamber heart
16. 3 vessel view
17. Interventricular septum
18. Bladder
19. Kidneys
20. Abdominal circumference
21. Fetal cord insertion
22. 3 vessel cord
23. Diaphragm

24. Extremities (including femur length, humerus length, hands, feet)

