### **2.4. Primary Outcome**

The primary outcome is the completion rate (number of scans that see all the views listed on pages 7 or 8 divided by total number of scans in that group) for first trimester ultrasounds, compared to the same metrics obtained in second trimester ultrasounds.

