#### Planes:

[figure not shown]
[figure not shown]
1. **Midsagittal fetus.** Landmarks required for optimal image: NT, nose, cord insertion, bladder
2. **Profile.** Landmarks required for optimal image: NT, nasal bone, maxilla

[figure not shown]
[figure not shown]
3. **Transventricular plane.** Landmarks required: bilateral symmetrical choroid plexus.
4. **Transthalamic plane.** Landmarks required: bilateral thalami, falx cerebri between anterior horns of the lateral ventricle.

[figure not shown]
[figure not shown]
5. **Transcerebellar plane.** Required landmarks: bilateral thalami, fourth ventricle.

[figure not shown]
6. **Orbital plane.** Required landmarks: bilateral orbits.

[figure not shown]
7. **Facial plane.** Required landmarks: bilateral orbits, bilateral maxillary processes.

[figure not shown]
[figure not shown]
[figure not shown]
8. **Four chamber view.** Required landmarks: two ventricles, two atria in diastole.

[figure not shown]
9. **Three-vessel-trachea view.** Required landmarks: V-shaped aorta/PA with same directional flow, trachea.

[figure not shown]
[figure not shown]
[figure not shown]
10. **Coronal trunk.** Required landmarks: stomach/diaphragm.  
11. **Retroperitoneum.** Required landmarks: bilateral kidneys

12. **AC.** Required landmarks: stomach, umbilical vein.
13. **Cord insert.** Required landmarks: cord insertion with abdominal skin away from adjacent tissue
14. **3VC.** Required landmarks: bladder, bilateral umbilical arteries using Doppler.

[figure not shown]
[figure not shown]

15. **Extremities.** Can be captured by imaging bilateral arms/hands, then bilateral legs/feet, or by imaging the right extremities together and the left extremities together. Required landmarks: four upper and four lower limbs. Can also be captured in 3D. (Fingers and toes not required.)

16. **Spine.** Required landmarks: entire spine with overlying skin not adjacent to any other structures.

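### The first-trimester scan is not described consistently: the Appendix 4 text omits a view that the primary outcome scores, the scan is given 15 or 25 minutes, and Section 7.1's own times contradict its claim of comparable exposure

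*Combined protocol and SAP*

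**What the plan says.** **Views.** Section 2.4 defines the primary outcome as the "number of scans that see all the views listed on pages 7 or 8", divided by all scans in the group. By the table of contents those pages hold Section 1.2.d, which lists 20 first-trimester items, including "Placental cord insertion", situs and a 3 vessel view. Section 1.2.d adds: "A detailed list of images required in the intervention is appended". The appended text is Appendix 4, with an initial survey, 16 numbered planes and some additional planes. Its cord plane asks for "cord insertion with abdominal skin away from adjacent tissue". Its great-vessel plane is a three-vessel-trachea view, with landmarks "V-shaped aorta/PA with same directional flow, trachea". It also has a coronal trunk plane ("Required landmarks: stomach/diaphragm").

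**Duration.** Section 4.3.b states: "After this detailed research ultrasound, which will be limited to 15 minutes". It expects about 30 minutes for all of that visit's scans. Section 7.1 gives the same research scan an estimate of 25 minutes. The screening scan is 5 minutes in Sections 3.2 and 4.3.a and 2 minutes in Section 7.1.

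**Exposure.** Section 7.1 says that fetuses in the two arms receive comparable ultrasound time and then lists planned times by arm. For the intervention arm these are 2, 25, 10 and 45 minutes; for the comparison arm, 2, 10 and 30.

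**The concern.** Scoring is all-or-nothing: one missing view makes a scan incomplete. If the operator works from Appendix 4 and the scan is scored on Section 1.2.d, a view can be missing because nobody was asked to obtain it. That acts on first-trimester completion, the rate that the trial expects to be higher (85% against 70%, Section 9.1) and the one tested by the interim rule in Section 3.5. The second-trimester list in Section 1.2.d also contains placental cord insertion. It is presented as a summary of the site's own second-trimester protocol, so the documents show no matching gap on that side, although that protocol is not included in full.

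The time limit bears on the same outcome, since a scan cut off before all views are seen counts as incomplete. It also bears on the scan-time outcome in Sections 2.5 and 9.2. If that outcome means this scan and the limit is enforced, it cannot exceed 15 minutes. If it means total time per woman, it is not capped in that way.

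The exposure sentence supports the safety argument. The theoretical fetal risk that the protocol names (judged low) concerns the first trimester, which is where the arms differ by design.

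**Working it through.** **1. Section 1.2.d list against the Appendix 4 text (figures not available).**

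- 17 items have a counterpart, some under another heading. Heart rate and head circumference fall in the initial survey (M-mode cardiac activity; HC), and bladder is a landmark of two planes.
- Placental cord insertion is not requested. The initial survey asks for placental position only, and plane 13 is the insertion at the fetal abdomen. The midsagittal plane also lists a cord insertion, but as a landmark of the fetus.
- Situs is not named. It may be partly inferable from the stomach and four-chamber planes.
- The 3 vessel view appears as a three-vessel-trachea view.
- Check: 17 + 1 + 1 + 1 = 20.
- In the other direction, coronal trunk is in the appendix only.

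**2. Duration.** The limit is 15/25 = 60% of the estimate. Taking the limited clinical scan as 10 minutes (Section 7.1):

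- Times from Sections 3.2 and 4.3: 5 + 15 + 10 = 30, which fits Section 4.3.b's total of about 30.
- Times from Section 7.1: 2 + 25 + 10 = 37, which does not.

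So Section 7.1 stands against Sections 3.2 and 4.3 on two durations. This does not show which set is right.

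**3. Exposure.** Planned minutes are screening + research scan (intervention arm only) + limited scan + second-trimester scan. Repeat scans are excluded.

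| Times used | Intervention | Comparison | Difference | First trimester |
|---|---|---|---|---|
| Section 7.1 as printed | 2+25+10+45 = 82 | 2+10+30 = 42 | 40 (ratio 1.95) | 37 vs 12 |
| Research scan 15 | 2+15+10+45 = 72 | 42 | 30 (ratio 1.71) | 27 vs 12 |
| Research scan 15, screening 5 | 5+15+10+45 = 75 | 5+10+30 = 45 | 30 (ratio 1.67) | 30 vs 15 |

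Of the 40 printed minutes, 45 − 30 = 15 come from the second-trimester scan. No reason is given for that difference, although Section 1.2.d evaluates both scans on one protocol and Section 6 keeps the clinical team unaware of assignment.

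Now assume the same second-trimester time g in both arms, with screening time s and research scan r:

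(s + r + 10 + g) − (s + 10 + g) = r

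The difference is then 15 or 25 minutes whatever s and g are, and all of it is in the first trimester. With s of 2 or 5 and g of 30 or 45, the ratio runs from 75/60 = 1.25 to 67/42 = 1.60.

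**The case against.** Several objections have force.

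- *Section 2.4 already fixes one scoring list.* It does. A reader might infer two competing definitions of the primary outcome; the documents do not support that. The mismatch is between what is scored and what the operator is told to obtain.
- *A time-limited scan is already scored.* Also true. A reader might infer that a rule is missing, but under Section 2.4 such a scan is incomplete if any view is lacking, and it stays in the denominator. Section 7.2 treats scans stopped for discomfort in the same way.
- *The appendix is partly pictorial.* Its figures are not available here and may show more than its text, so the finding concerns the text only.
- *The three-vessel difference may be one of wording.* The documents do not define one view against the other, so it cannot be called a different view on their evidence.
- *The limb landmark is readable.* A reader might infer that "four upper and four lower limbs" cannot be met in a singleton. The same item speaks of arms with hands and legs with feet, so two arms plus two hands, and two legs plus two feet, is a natural reading. It needs clearer wording, no more.
- *The exposure sentence is explained by scan counts, and the minutes are printed below it.* The parenthesis does count scans, and nothing is hidden. But the sentence is about time, and the minutes contradict it.
- *Minutes are not dose.* This stands. The End Points – Safety section ties the theoretical risk to high-output techniques such as color Doppler, and no Doppler time is given. Repeat second-trimester scans are allowed in both arms, so 1.95 is a ratio of planned times and not of actual exposure.

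**Conclusion.** The point holds in three parts.

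1. The Appendix 4 text does not request one scored view, does not name a second, words a third differently and adds one plane. Under all-or-nothing scoring, an unrequested view can only lower first-trimester completion. It also feeds the stopping rule, assuming that Section 3.5 judges scans on the same list. A reader might infer that this could erase the planned advantage. That would need 1 − 0.70/0.85 = 17.6% of otherwise complete scans to lack the view, and the documents give no figure for that fraction. The direction is known; the size is not.
2. The same scan is limited to 15 minutes in one section and estimated at 25 in another. The effect on completion and on the scan-time outcome cannot be quantified from the documents.
3. The statement of comparable exposure is contradicted by its own section: 82 against 42 planned minutes, or 72 against 42 with the 15-minute limit. The first-trimester excess is 15 to 25 minutes under either printed duration. A reader might infer a safety hazard; the documents support only that the sentence is inaccurate.

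This should be corrected. It does not touch the sample size or the main test.

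**What to change.** - Make the Section 1.2.d list and Appendix 4 agree, so that one list both directs the operator and defines a complete scan. Settle placental cord insertion, situs, the three-vessel wording and coronal trunk before analysis, and clarify the limb landmark at the same time.
- If scans have already been done to the appendix, fix how the unrequested view is scored before analysis and without reference to results.
- Reconcile the scan times in Sections 3.2, 4.3 and 7.1, including the 45 and 30 minutes for the second-trimester scan.
- Say in Section 2.5 whether the scan-time outcome is this scan alone or total time per woman.
- Replace the exposure sentence in Section 7.1 with the reconciled totals per arm, overall and for the first trimester.

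Which list and which times are right is for the sponsor to decide. The cost is wording plus, if needed, one scoring rule. The downside is a less favourable exposure statement.
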